A technology navigator will monitor daily compliance and check-in with participants to assist with login credentials, lost or damaged devices, cellular connectivity, difficulties using the phones or breathalyzers, and intentional non-use of the breathalyzers—with close monitoring during the first week. Navigators will monitor for safety issues and IPV (interpersonal violence) during routine check-ins and will provide assistance should a safety/IPV issue arise.

5.11 Survey assessments. Assessment visits will be held in community-based locations such as youth centers or in our team's mobile caravans used in other couples' studies. To minimize loss-

Couple-Based Motivational Interviewing with Mobile Breathalyzers to Reduce Alcohol Use in South Africa

to-follow-up, we will administer follow-up surveys over the phone in the case that a participant moves out of the area or is unavailable for an extended period of time. For the pilot study, surveys will be administered at baseline and 2-months (after receiving all MI sessions and/or using the breathalyzers for 60 days), and 6-months post-intervention initiation. Measures collected will be the same across visits with the exception of time-invariant variables such as demographics (collected at baseline only). All measures will be pre-tested, tailored for South Africa, and translated to *isiZulu* and back-translated to English. See Appendix with full survey instrument. Survey assessments will be interviewer-administered on tablet devices using REDCap mobile, last around 90 minutes, and uploaded to a secure web-based storage system. Partners will be assessed separately, but simultaneously, in private interview rooms.

	Domain	Measure (alphas noted are from prior studies with couples)
Primary outcomes (future trial)	Alcohol use	Number of drinking days in past 21, assessed using the three-week timeline follow-back method (TLFB) confirmed with the PEth biomarker.[32] AUDIT-C positive (score of ≥ 4 for men and ≥ 4 for women) and/or PEth positive (≥ 35 ng/ml).[33, 34]

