by requesting clinical files from patients' HIV clinic. Participants will be asked to bring their clinic cards to study visits, which contain identifiers that can be used to look up HIV test results.

5.13 Blood samples. At screening, we will obtain consent to confirm HIV status for all participants who report being positive using a point-of-care test. We will have results in 10-15 minutes. We will base eligibility on the result of this test. We will only test potential participants who report living with HIV. We will not return test results. ***At the two-month follow-up visit, we will collect blood samples via finger pricks for testing using DBS cards. Participants who are heavy drinkers will be tested for PEth. Participants who are heavy drinkers and living with HIV will have their viral load tested.*** PEth is 95% sensitive and 73% specific for detecting heavy drinking in the past 21 days and is highly correlated with number of drinking days among PLWH in SSA. PEth samples will be processed at the United States Drug Testing Laboratories using liquid chromatography tandem mass spectrometry. PEth samples on DBS cards will be stored at the HSRC research center until they can be batch transported to the US laboratory. PEth results will be reported as positive/negative and in ng/ml. Viral load DBS samples will be processed at the Universal Pathology Laboratory (UPL) in South Africa or an HPTN Network Laboratory certified laboratory facility. Viral load DBS samples will be processed using the Aptima HIV-1 Quant Dx Assay (DBS supplement) with a lower limit of detection of 30 copies/ml. In line with standard clinical practice in South Africa, less than 1000 copies/ml will be the threshold for viral suppression.

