7.3 Hypotheses and methods for preliminary/exploratory analyses. Although the purpose of this study is to determine F&A rather than to conduct formal hypothesis tests, we will evaluate exploratory hypotheses as part this assessment process. For example, we expect that: H1) participants in the couples MI-only group (arm 2) will report a greater reduction in the number of drinking days (confirmed with PEth) than participants in the control group (arm 1); H2) participants in the couples MI with mobile breathalyzers group (arm 3) will report a greater reduction in the number of drinking days than participants in the couples MI-only group (arm 2). Secondarily, we also anticipate that intervention participants will report a higher odds of adherence to ART and viral suppression than those in the control arm. We also anticipate the intervention participants will report higher (indicating more positive) scores on communication and relationship dynamics and less intimate partner violence than those in the control arm. Reflecting the exploratory nature of these analyses, alpha will be set at .05 for all inferential analyses.

7.4 Power analyses. Formal tests of health outcomes or attempts to obtain valid estimates of effect sizes are not statistically justified for the proposed study. Pilot studies, by design, cannot definitively test hypotheses due to their smaller sample sizes and the frequent design adjustments necessary to maximize recruitment, retention and quality assessment of outcomes. Effect size estimates are not sufficiently reliable given the breadth of the confidence intervals. However, to supply additional information, we conducted several power analyses using NCSS PASS. In sum, our study is powered to detect small to medium distances to confidence limits for descriptive statistics and medium to large longitudinal analysis effects, though, as noted above, formal hypothesis testing will not be the focus of this F&A study.

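### The PEth schedule is inconsistent between sections; if section 5.13 governs, PEth can support a month-2 comparison between arms but cannot confirm a reduction from baseline

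*Combined protocol and SAP*

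**What the plan says.** Section 5.13 is the only place that gives blood-spot collection a time: "At the two-month follow-up visit, we will collect blood samples via finger pricks for testing using DBS cards". It adds "Participants who are heavy drinkers will be tested for PEth", without saying when heavy drinking is judged. The only earlier blood test it describes is for HIV: "At screening, we will obtain consent to confirm HIV status for all participants who report being positive using a point-of-care test".

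Two other sections point elsewhere. Section 3.1 has both partners in couples with two heavy drinkers on ART giving blood at follow-up visits, in the plural. Section 5.11 says "Measures collected will be the same across visits", apart from time-invariant items, and the outcome table in that section names PEth. The visits are baseline, 2 months and 6 months (section 3.3).

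The table in section 5.11 gives two alcohol outcomes, both labelled as primary outcomes of a future trial:
- drinking days in the past 21 by timeline follow-back (TLFB), confirmed with PEth;
- a combined outcome, positive if AUDIT-C is positive and/or PEth is at least 35 ng/ml. The AUDIT-C cut-off is 4 for men and 4 for women.

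At entry (section 3.1) the AUDIT-C cut-off is 4 for men and 3 for women.

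H1 in section 7.3 states that the MI-only arm "will report a greater reduction in the number of drinking days (confirmed with PEth) than participants in the control group". H2 states that "participants in the couples MI with mobile breathalyzers group (arm 3) will report a greater reduction in the number of drinking days" than the MI-only arm, and does not mention PEth.

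**The concern.** A reduction needs two time points. Under section 5.13, PEth exists at one. A reader of H1 would expect the biomarker to back the reported fall in drinking, and this schedule cannot supply that.

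The combined outcome also changes meaning with the visit: where PEth is taken there are two ways to be positive, and where it is not there is one. Anyone setting month 2 beside month 6 would be comparing two definitions.

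The plan is a pilot, and Aim 2 is to develop and test the procedures and instruments for a later trial. An unsettled biomarker schedule and outcome definition could be carried into that trial.

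**Working it through.** The plan states no power, effect size or standard deviation that depends on PEth, so there is no figure of its own to reproduce. The check sets the passages side by side and then sizes what remains.

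**1. PEth by visit**
- Baseline: not scheduled in 5.13; implied only if 5.11 is read literally.
- Month 2: scheduled in 5.13.
- Month 6: not scheduled in 5.13; implied by the plural in 3.1 (for one type of couple) and by 5.11.

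The three sections cannot all be right as written.

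**2. What H1 keeps if 5.13 governs**
- TLFB days come from the survey at every visit, so the contrast between arms in reported reduction is available.
- Month-2 PEth can be compared between randomised arms without a baseline value.
- A within-person fall confirmed by PEth is not available.

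**3. Precision of the month-2 PEth comparison**
- Continuous PEth, 80% power, two-sided 0.05 (sidedness assumed): detectable difference = (1.96 + 0.84) × √(2/n) SD. For n = 30 per arm (section 2.5) this is 0.72 SD. For n = 25, close to the 85% retention threshold in Table 4 (0.85 × 30 = 25.5), it is 0.79 SD.
- PEth positive or negative: section 5.13 says "PEth is 95% sensitive and 73% specific for detecting heavy drinking in the past 21 days". Assume this holds at 35 ng/ml and that a share h of 0.4 to 0.7 is truly drinking heavily. The positive share is p = 0.95h + 0.27(1 − h), which is 0.542 at h = 0.4 and 0.746 at h = 0.7. The 95% half-width is 1.96 × √(2p(1 − p)/30), which is 25.2 and 22.0 percentage points. On the same assumption, a true 10-point difference appears as 10 × (0.95 + 0.73 − 1) = 6.8 points.

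**4. Combined outcome by visit**
- Month 2 is AUDIT-C or PEth; month 6 is AUDIT-C alone. Adding a second route can only keep or raise the positive share. So, for the same drinking and the same AUDIT-C answers, month 2 reads at least as high as month 6.
- At baseline a male index patient has an AUDIT-C of 4 or more by eligibility. Unless his baseline survey score differs from screening, he is already positive and PEth could not change that.
- The size of the month-2 to month-6 gap cannot be derived: the plan gives neither the share drinking heavily nor the accuracy of AUDIT-C.

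**5. Women's cut-off**
A woman who enters with a score of 3 meets section 3.1 but is AUDIT-C negative under section 5.11 from the start. Only women scoring exactly 3 are affected, probably few: section 3.1 says the primary drinker in this community is almost always the man.

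**6. Who is tested**
Sections 3.1 and 3.2 imply that heavy-drinker status is set at entry. If it were judged at month 2, being tested would depend on the outcome. Phone follow-up, allowed in 5.11, yields no blood spot.

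**7. Drinking days**
Assume equal variances at the two visits and correlation r between them. Relative to the single-visit variance, a change score has 2(1 − r) and a baseline-adjusted comparison has 1 − r². The ratio is (1 − r²)/(2(1 − r)) = (1 + r)/2:
- r = 0.3: 0.65
- r = 0.5: 0.75
- r = 0.7: 0.85

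The adjusted analysis therefore has 15-35% lower variance. Also, H1 and H2 refer to participants without limiting them to index patients. If both partners are analysed and the other partner does not drink (assumed), a mean difference d becomes (d + 0)/2 = d/2.

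**The case against.** A reader might infer that H1 cannot be tested at all. The documents do not support that. H1 is a contrast between arms in reported drinking days, and no passage promises a fall in PEth itself. Confirmation may mean only that reports at follow-up are checked against the biomarker, which is a fair reading of section 5.11, and randomisation makes the month-2 PEth comparison valid. All of this stands. What is left is that the wording of H1 allows more than 5.13 can deliver.

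A reader might also take 1 − 0.73 = 27% as the chance that someone who has stopped heavy drinking is counted positive at month 2 but not at month 6. That figure is purely assumed. The documents do not tie the stated specificity to 35 ng/ml, and it requires AUDIT-C to have no false positives. It should not be used as a bias estimate.

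No hypothesis in 7.3 uses the combined outcome and no analysis of its trend is planned. That stands, and limits the consequence to how the outcome is described and later read.

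The plan disclaims inference: "Formal tests of health outcomes or attempts to obtain valid estimates of effect sizes are not statistically justified for the proposed study". That is a fair reason to keep the point modest, but section 7.3 still sets alpha at .05 for its exploratory tests.

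Finally, the plan names no change-score test, so the variance gain is measured against one natural reading of a reduction, not against a stated method. The women's cut-off and the choice of analysis population do not follow from the PEth schedule; they are separate corrections to the same outcomes.

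**Conclusion.** The point holds as an inconsistency that should be resolved. Sections 3.1, 5.11 and 5.13 disagree on when PEth is taken, and no passage explicitly schedules a baseline sample. If 5.13 governs, the biomarker supports corroboration of self-report and a comparison between arms, both at month 2 only. That comparison is valid but descriptive: roughly 0.72-0.79 SD detectable, or a half-width of 22-25 points under the assumed accuracy and prevalence. The combined outcome is then not comparable between months 2 and 6. For male index patients the baseline matters little.

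The mismatch in the women's cut-off (3 against 4) is certain on the page and small in effect.

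Only exploratory outcomes are affected. The primary objective is feasibility and acceptability (section 7.2), and no threshold in Table 4 uses PEth.

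**What to change.** 1. Reconcile sections 3.1, 5.11 and 5.13 in one table of PEth by visit and by person. Reconcile the women's AUDIT-C cut-off between 3.1 and 5.11.
2. If PEth stays at month 2 only, word H1 as the TLFB reduction, with PEth as a month-2 comparison between arms, and report the combined outcome at month 2 only. If the reconciled schedule includes other visits, use the combined outcome only at visits with PEth.
3. State in 5.13 that month-2 PEth testing follows heavy-drinker status at entry, whatever is reported at month 2. Report by arm the number without a sample, including those followed up by phone.
4. Analyse H1 and H2 in index patients, comparing follow-up drinking days adjusted for the baseline drinking days already collected.

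With PEth kept at month 2, the cost is protocol and analysis wording, with no added visits or samples. The downside is that the biomarker-supported claim is then limited to a month-2 difference between arms.

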5.14 Exit interviews

Sampling: To contextualize the feasibility and acceptability data, we will conduct 60-90 minute exit interviews with 15 couples at the 2-month follow-up. Around five couples will be recruited from each arm, purposively sampled by participation level. For Arm 2, participation will be categorized as: low=attended one MI session, medium=attended two sessions, and high=attended all three sessions. For Arm 3, we will aim to enroll couples with varying test completion rates, categorized as low=completed less than 70% of breathalyzer tests, medium=completed 70-85% of tests, and high=completed>85% of tests. We will also try to interview couples in which both partners were heavy alcohol users to further understand how the intervention impacts dual drinkers.

Interview questions: We will elicit information on intervention preferences and satisfaction with domains of the intervention (e.g., frequency of breathalyzer tests and MI sessions, length, content, format of MI sessions). To explore dyadic mechanisms of change, we will elicit information on whether and how the breathalyzers and MI sessions enhanced communication, communal coping, and support. We will also elicit information on technology issues (e.g., user app experience, network connectivity, load shedding and power outages, battery life, trouble with logins) and contextual issues (e.g., literacy, alcohol stigma). Given the central question of whether the mobile breathalyzer technology can be used with couples to trigger support, we will assess how knowledge of BAC levels impacts the relationship (e.g., increases in couple conflict, changes in communication), how both partners interpret and respond to BAC levels, and the types of partner support provided and when.

Couple-Based Motivational Interviewing with Mobile Breathalyzers to Reduce Alcohol Use in South Africa

Procedures: Given the gender-power dynamics in this setting, the PI [name]'s prior qualitative research, and the potential bias (e.g., women not feeling comfortable voicing their opinions in front of male partners) and increased risk for violence that could result from interviewing partners together, we will interview both partners separately, but simultaneously. Interviews will be audio-recorded, transcribed word-for-word, and translated from *isiZulu* to English, and imported into Dedoose for analysis.

Analysis: We will use our successful analysis approach developed for dyadic qualitative data. This consists of coding one couple at a time by assigning new and *a priori* codes to both partners' transcripts. We will write an analytic memo for each couple that summarizes key factors involved, key themes or constructs, and within-couple consistencies and discrepancies. We will code the next set of couple transcripts and write an analytic memo for that couple and repeat this process until all transcripts are coded and 15 couple memos are written. We will construct data matrices to compare and contrast codes and themes between couples. An investigator meeting will be held to review the emergent patterns/themes, in conjunction with the quantitative findings, and to identify any final modifications to the intervention.

6.0 Safety monitoring and adverse event reporting

6.1. Safety monitoring

Safety-related risks could consist of: 1) loss of confidentiality; 2) loss of privacy; 3) couple tension, conflict and/or violence, and coercion; 4) discomfort or distress as a result of the personal and sensitive nature of the interviews or intervention sessions on alcohol, relationship dynamics, and violence; and 5) risks associated with finger pricks to collect blood samples for viral load and alcohol biomarkers (Phosphatidylethanol, or "PEth").

Any incidents involving subject safety will be reported to both institutional IRBs (Human Sciences Research Council and The University of California, San Francisco by the PI within 10 working days. The following information will be included in any report: 1) all serious adverse events associated with study procedures and/or 2) any events or problems involving the conduct of the study or patient participation, including problems with the recruitment or consent processes. The US PI will also provide a description of any problems or issues observed in the course of the study to each IRB on an annual basis.

Safety monitoring procedures. All safety-related risks will be monitored routinely at the time of assessment or intervention sessions. Procedures are in place to protect the confidentiality of information from one's partner and to monitor any confidential information. Interviewers and intervention staff will be trained to increase their sensitivity and present a caring and non-threatening manner regarding topics such as sexuality, HIV, and relationship issues. At any sign of discomfort or distress, or by request, interviews will be stopped. Confidentiality will be assured to participants at the time of consent, and they will be assured their answers or responses cannot be used against them for any reason, or for denial of any medical treatment. Standardized procedures will be documented and reviewed with staff regarding the possibility of tension, conflict or violence between partners. Procedures will be in place to monitor and respond to any instances reported by the participants of any type of negative relationship event, and proper action will be taken, including staff intervention and/or provision of referral for services depending on the level of the event (e.g., relationship conflict, an episode of domestic violence,

Couple-Based Motivational Interviewing with Mobile Breathalyzers to Reduce Alcohol Use in South Africa

etc.). If a participant is referred to outside services, they will be provided with a formal referral letter.

Safety-related risk reporting and action plan. Interviewers and intervention staff at HSRC will report any breach of confidentiality incurred by the participants to the UCSF project coordinator, who will then inform the site PI and the US PI. Any participant in need of treatment due to distress, relationship conflict, or alcohol issues will be referred for appropriate services following staff completing the study protocol pertaining to these situations. As indicated above, in the event that a participant is referred to outside services, they will be provided with a formal referral letter. The US PI will ultimately be responsible for informing the IRBs and the DSMB through the IRB adverse event reporting procedure, and the Project Office through immediate email of any life-threatening incident, and through annual reports of other incidents. In the event of any adverse or life-threatening events occurring at an unacceptable level, the US PI will take appropriate action to halt the study, release a participant from the study, or modify the study procedures to reduce or eliminate the identified risk.

6.2. Adverse events

Any adverse events following participation will be tracked via referral and clinician follow-up. We will adapt the standard HSRC adverse event form adverse event form to document the incident, actions taken, supervisor notes, and follow-up steps. This form, supplemented by any additional staff notes will be provided to the appropriate agencies, including the University of California, San Francisco and HSRC Research Ethics Committees and the funding agency (NIH, USA). Any resulting recommendations from the IRB will be communicated to NIH. The site PI will be responsible for monitoring and reporting of any adverse events to the US PI, and will involve the DSMB as described below.

6.3. Data Safety and Monitoring Board

The level of risk from this behavioral intervention trial is minimal. We have developed the following plan to monitor the trial and to deal with data and safety monitoring. A Data and Monitoring Safety Board (DSMB) consisting of HIV behavioral and international research experts will be assembled.

The DSMB will meet using a video-conference platform such as Zoom. The DSMB will approve the overall protocol, assessments, and consent forms. All reports of adverse events (AE) will be reported to them, as well as to the IRBs (UCSF and HSRC). Severe adverse events (SAE) will trigger an immediate meeting of the DSMB. Additional meetings will be arranged as needed, following any emergent AE issues. The DSMB will review all accrued data to assess whether the study aims were met and to ensure that the benefits of the intervention outweigh any harm.

7.0 STATISTICAL CONSIDERATIONS

7.1 Analysis of FGDs to refine the intervention. Using a template analysis approach [50], we will develop a pre-determined template based on elements of the intervention to retain or refine, and new elements to add to address the needs of the target population. Study investigators will generate a draft of the template with thematic codes for relevant domains of the intervention, and will independently code the FGD transcripts. The investigative team will then discuss the emerging themes, identify areas for further adaptation, and refine the intervention manual. Depending on the extent of the changes, we may hold a meeting with HSRC's CAB to review

Couple-Based Motivational Interviewing with Mobile Breathalyzers to Reduce Alcohol Use in South Africa

the FGD findings and identify intervention content and procedures that need to be added, removed, or refined.

7.2 Feasibility and acceptability data analysis. Our primary objective is to evaluate F&A of the intervention and study procedures. The primary analyses will include descriptive statistics of F&A indicators, comparing each statistic (e.g., percent retained) to the threshold listed in Table 4. Above-threshold findings will suggest a reasonable level of F&A while below-threshold findings would suggest that remedial modifications to study procedures and/or design would be required prior to moving forward with a full-scale trial. We will stratify the statistics by gender to consider sex as a biological variable.

Couple-Based Motivational Interviewing with Mobile Breathalyzers to Reduce Alcohol Use in South Africa

Table 4. F&A Domain	Measure	Threshold	Arm(s)
Recruitment	Number of couples enrolled per week	Average 5 per week/20 per month	All
Enrollment	Proportion of eligible couples who enroll and complete baseline assessment	80% of eligible couples will complete enrollment	All
Randomization	Proportion of enrolled couples who complete randomization process	90% of enrolled couples will complete randomization	All
Participation	Proportion of couples who attend 66% and 100% of MI sessions	100% of couples will attend 66% (2 out of 3) of sessions; 75% of couples will attend all 3 sessions	2, 3
Engagement with mobile breathalyzer technology	Proportion of breathalyzer tests taken after prompted; number of partner SMS messages sent and received on BAC results; number of drinker SMS reminders to take breathalyzer tests sent and received; average length of time to take breathalyzer tests after prompted; average number of app logins per week to access BAC data (for both partners); average user session length; number of lost/stolen phones and breathalyzers	70% completion rate	3
Retention	Retention rates; reasons for dropouts	85% retention at 2-month follow-up	All
Process outcomes	Length of MI sessions in minutes	≤90 minutes per session[9]	2, 3
Intervention fidelity	Expert ratings of quality of intervention using audio-recorded intervention sessions (checklists)	>80% inter-rater reliability	2, 3
Assessment procedures	Length of surveys; proportion of couples who complete baseline, 1, 2, and 6-month surveys	90 minutes; 75% of all couples will complete all assessments	All

Couple-Based Motivational Interviewing with Mobile Breathalyzers to Reduce Alcohol Use in South Africa

Acceptability	Proportion of couples satisfied with the intervention. Couples will decide their satisfaction together since this is a dyadic intervention.	75% of couples reporting being satisfied or very satisfied	All
---------------	---	--	-----

Couple-Based Motivational Interviewing with Mobile Breathalyzers to Reduce Alcohol Use in South Africa

7.3 Hypotheses and methods for preliminary/exploratory analyses. Although the purpose of this study is to determine F&A rather than to conduct formal hypothesis tests, we will evaluate exploratory hypotheses as part this assessment process. For example, we expect that: H1) participants in the couples MI-only group (arm 2) will report a greater reduction in the number of drinking days (confirmed with PEth) than participants in the control group (arm 1); H2) participants in the couples MI with mobile breathalyzers group (arm 3) will report a greater reduction in the number of drinking days than participants in the couples MI-only group (arm 2). Secondarily, we also anticipate that intervention participants will report a higher odds of adherence to ART and viral suppression than those in the control arm. We also anticipate the intervention participants will report higher (indicating more positive) scores on communication and relationship dynamics and less intimate partner violence than those in the control arm. Reflecting the exploratory nature of these analyses, alpha will be set at .05 for all inferential analyses.

7.4 Power analyses. Formal tests of health outcomes or attempts to obtain valid estimates of effect sizes are not statistically justified for the proposed study. Pilot studies, by design, cannot definitively test hypotheses due to their smaller sample sizes and the frequent design adjustments necessary to maximize recruitment, retention and quality assessment of outcomes. Effect size estimates are not sufficiently reliable given the breadth of the confidence intervals. However, to supply additional information, we conducted several power analyses using NCSS PASS. In sum, our study is powered to detect small to medium distances to confidence limits for descriptive statistics and medium to large longitudinal analysis effects, though, as noted above, formal hypothesis testing will not be the focus of this F&A study.

